### **5.2 Safety Overview**

M207 consisting of two patches of 1.9 mg (3.8 mg), 30 minute upper arm application, has been studied in healthy volunteers (in clinic) and subjects with migraine (outpatient). This regimen has been generally well-tolerated, with adverse events observed (dizziness and chest tightness) of those typically reported for triptans. Adverse events reported were almost always within the first few minutes after patch application. It is anticipated that systemic exposure with forearm application will be not significantly different than that seen with upper arm application, based on our experience with glucagon. Also, since Cmax was generally observed, on average, at around 15 minutes, wearing the patches for 1 hours will probably not be associated with higher Cmax levels than 30 minutes and should not result in different tolerability issues.

## **6.0 Study Populations (Definition of Populations for Analysis)**

### **6.1 Pharmacokinetic Population**

PK population is defined as below:

- Concentration data of subjects, who complete at least two periods of the study, will be included in the pharmacokinetic and statistical analysis. Concentration

and pharmacokinetic data of other subjects will be presented in the report if available, but will not be included in the statistical analysis.

- Data from any subject with missing concentration values in any period (like missed blood samples, lost samples, samples unable to be quantitated) may be used for bioavailability evaluation if pharmacokinetic parameters can be reliably estimated using the remaining data points otherwise that specific pharmacokinetic parameter data will be excluded from the bioavailability evaluation.
- If any subject has all BLQ/zero values in any period, then the subject will be excluded from the bioavailability evaluation analysis from that particular period.
- If the pre-dose concentration appears to be >5% of the Cmax in any subject in any period, then the subject will be excluded from the statistical analysis in that period.
- Kel and related elimination phase parameters will not be estimated for cases that do not exhibit a terminal log-linear phase in the concentration versus time profile.

## **6.2 Safety Population**

Safety analysis will be performed on all randomized subjects receiving at least one dose of investigational product. Subjects' safety data will be presented according to the treatment they actually received.

Drop-outs within a 24-hour period are not anticipated; however should they occur prior to 2 hours after patch application then additional eligible subjects may be enrolled.

## **7.0 Incomplete and Missing Data**

No adjustment or imputation will be utilized for missing values or for subjects who withdraw prior to completing the study. In case of missing data for skin assessment, LOCF (last observation carried forward) method will be used.

## **8.0 Study Subjects and Conduct**

Subject accountability will be tabulated for each study treatment and for all subjects combined by summarizing the number of subjects who are randomly assigned to treatment, complete the study, prematurely discontinue, and the reason for discontinuation. A listing will be presented to describe dates of withdrawal and the reason for discontinuation for each discontinued subject. A listing of study treatment administration will be provided.

## **9.0 Demographic Characteristics**

Individual subject demographics will be presented in listings. Demographic characteristics such as age, gender, race, ethnicity, height, weight and body mass index (BMI) will be summarized and tabulated for all randomized subjects. Descriptive statistics will be presented for age, height, weight and BMI. Frequency counts and percentage will be presented for gender, race and ethnicity.

## 10.0 Prior and Concomitant Medications

Subjects will be asked to refrain from taking either prescription or OTC medications from the time of Screening until the completion of the study, except for those discussed in this section. All concomitant medications taken during the study will be recorded on the concomitant medications case report form (CRF) with indication for use, totally daily dosage, and dates of drug administration.

Subjects must discontinue use of herbal or over-the-counter medications (with the exception of all medications listed below) for 48 hours prior to treatment days and throughout the study.

If the medication end date is known and medication end date is prior to the first dose of study treatment it will be classified under prior medication. If the end date of the medication is unknown, it will be considered as concomitant medication. A subject listing of all prior and concomitant medications and related information (e.g.: dose, unit, frequency etc.) will be presented.

## 11.0 Pharmacokinetic Analysis

Pk analysis will be performed on the pharmacokinetic population (see section 6.1).

All Below Limit of Quantitation (BLQ) concentration values will be set to zero before pharmacokinetic analysis, except in the case where there is a measurable value immediately preceding the BLQ value and a measurable value immediately after the BLQ value. In these instances, the BLQ value will be set to missing.

The actual time of blood collection for all samples collected will be used in the calculation of pharmacokinetic parameters.

*Pharmacokinetic parameters:* The following pharmacokinetic parameters will be determined from the time and concentration data using a non-compartmental analysis of WinNonlin® professional software (Phoenix® version 6.4 or higher; Pharsight Corporation, USA).

Cmax: Maximum measured plasma concentration over the time span specified.

Tmax: Time of the maximum measured plasma concentration. If the maximum plasma concentration occurs at more than one time point, the first is chosen as Tmax.

AUCt: The area under the plasma concentration versus time curve will be calculated using the linear trapezoidal rule from the zero time point to the last quantifiable concentration.

AUCi: The area under the plasma concentration versus time curve from zero to infinity will be calculated by adding Ct/Kel to AUCt, where Ct is the last quantifiable concentration and Kel is the elimination rate constant.

AUC(0-30mins): The area under the plasma concentration versus time curve will be calculated using the linear trapezoidal rule from the time zero to 30 minutes.

AUC(0-60mins): The area under the plasma concentration versus time curve will be calculated using the linear trapezoidal rule from the time zero to 60 minutes.

AUC(0-120mins): The area under the plasma concentration versus time curve will be calculated using the linear trapezoidal rule from the time zero to 120 minutes.

Kel: The terminal elimination rate constant will be obtained from the slope of the line, fitted by linear least squares regression, through the terminal points of the log (base e) of the concentration versus time plot for these points.

tHalf: The half-life will be calculated by the equation  $t_{Half} = 0.693 / K_{el}$

AUC\_%Extrap\_obs: The residual area in percentage will be determined by the formula,  $[(AUC_i - AUC_t) / AUC_i] \times 100$

Frel – Relative Bioavailability.

Bioavailability relative to other treatment sites of application and wear times will be calculated using the below mentioned formula;

**Formula for calculation of Frel;**

**Frel = 100\*(AUCx\*Dy) / (AUCy\*Dx);** where relative bioavailability measures the bioavailability (estimated as the AUC) of a treatment-X when compared with treatment-Y of the same drug. **D** is the dose administered.

Frel will be calculated for AUCt.

Ratios will be reported for AUC(0-30mins), AUC(0-60mins), AUC(0-120mins), AUCt, AUCi and Cmax.

No value of Kel, AUCi or tHalf will be reported for cases that do not exhibit a terminal log-linear phase in the concentration versus time profile.

- *Descriptive statistics:* Mean, standard deviation, coefficient of variance, Median, Maximum and Minimum for applicable pharmacokinetic parameters will be calculated.

- *Statistical analysis:* Statistical analysis will be performed on pharmacokinetic data of subjects using SAS® statistical software (Version: 9.4 or higher; SAS Institute Inc, USA).
- *Analysis of Variance:* Ln-transformed data of Cmax, AUC(0-30mins), AUC(0-60mins), AUC(0-120mins), AUCt and AUCi will be evaluated statistically using the PROC MIXED procedure from SAS® for difference due to treatment, with period and sequence as a fixed effects and subject within sequence as a random effect.

All main effects will be tested at 5% level of significance using the Mean Square Error as the error term.

- Two one-sided 90% confidence intervals for the ratio of means between drug formulations will be calculated for Ln-transformed data of Cmax, AUC(0-30mins), AUC(0-60mins), AUC(0-120mins), AUCt and AUCi.

The data of metabolite n-desmethyl zolmitriptan will be provided as supportive information.

The comparisons of interest will be treatment A vs. B, A vs. C, A vs. D, B vs. C, B vs. D and C vs. D.

## 12.0 Assessment Details

### Clinical Laboratory Tests

Standard clinical laboratory tests (serum pregnancy for all women, CBC, hematology, and urinalysis) will be performed at Screening and End of Study (or early termination) and urine pregnancy testing for all women at each Admission/baseline visit.

A blood sample at screening will be taken to perform serological tests for HIV, Hepatitis B and Hepatitis C.

Urine drug screen and alcohol (breath) testing will be performed at screening and each Admission/baseline visit. Urine drug screen will test for amphetamine, barbituates, cocaine, cannabinoids, phencyclidine (PCP), opioids, and methamphetamines.

Samples will be analyzed by a local laboratory.

### Vital Signs

Vital signs include heart rate, pulse, respiratory rate, as well as systolic and diastolic arterial pressure. Vital signs will be recorded after subjects have been in the seated resting position for 2 minutes. Temperature will be taken at Screening, admission/baseline, and at end of study visit/or early termination only.

### Electrocardiograms

A standard 12-lead ECG will be performed by a qualified individual at the site. General morphology and intervals [Heart rate, QRS, PR interval, QRS, QTn, QTcf], of interest will be assessed with each tracing. The principal or sub-investigator must review the tracing and assess it for any clinically significant abnormality.

### **Investigator Visual Skin Assessments of the Application Sites**

Each M207 patch site (where a patch has been removed) will be observed for the following skin assessments pre-dose and immediately after removal of the patches from the subject's skin (and before swabbing) at 30 min (for 30 min wear time treatment groups only), 60 min, 12 hr, 24 hr and at the End of Study/or Early Termination visit.

#### **Erythema**

The erythema evaluations will be performed using the following scale:

- 0 = None
- 1 = Mild redness
- 2 = Moderate colored redness
- 3 = Beet colored redness

#### **Edema**

The edema evaluations will be performed using the following scale:

- 0 = None
- 1 = Slight edema
- 2 = Moderate edema
- 3 = Severe edema

#### **Bruising**

Bruising assessments (visual rating) will be performed using the following scale:

- 0 = None
- 1 =  $\leq 25\%$  application site has bruising spots
- 2 =  $\geq 26$  to  $\leq 50\%$  application site has bruising spots
- 3 =  $> 50\%$  application site has bruising spots

#### **Bleeding**

Bleeding will be assessed using the following scale:

- 0 = None
- 1 = Pink color on skin
- 2 = Visible blood drop
- 3 = Active bleeding

For example;

Skin assessment score presented in Table-A will be modified as presented in Table-B for statistical analysis using LOCF method.

**Table-A**

Subject	Skin assessment scoring_ Time Points(Hrs)				
	0.0	30 minutes	60 minutes	12 hour	24 hour
1	0	0	0	2	2
2	0	2	2	3	Missing
3	0	1	2	2	Missing

**Table-B**

Subject	Skin assessment scoring_ Time Points(Hrs)				
	0.0	30 minutes	60 minutes	12 hour	24 hour
1	0	0	0	2	2
2	0	2	2	3	3
3	0	1	2	2	2

### Patch Adhesion Assessment

Patch adhesion assessment at the time of application and at 30 min and 60 min post-dose (for 60 min wear time treatment group only) will be checked for the degree of adhesion by investigators should use a 5-point numerical scale in which each score corresponds to a specified range of adhered surface area of each patch, as follows:

0 =  $\geq$  90% adhered (essentially no lift off the skin)

1 =  $\geq$  75% to  $<$  90% adhered (some edges only lifting off the skin)

2 =  $\geq$  50% to  $<$  75% adhered (less than half of the patch lifting off the skin)

3 =  $>$  0% to  $<$  50% adhered (not detached, but more than half of the patch lifting off the skin without falling off)

4 = 0% adhered (patch detached; completely off the skin).

For example;

### **Adhesion Data:**

Actual Adhesion score presented in below Table;

Subject	Adhesion scoring_Time Points(Hrs)		
	0.0	30 minutes	60 minutes
1	0	0	0
2	0	2	2
3	0	1	1

### **13.0 Subject Disposition**

An overall summary of subject's disposition will be presented using a clear accounting of all subjects who entered the study, subjects who completed the study and subjects who do not complete the study, along with the reason of not completing the study. Randomized subjects who do not complete the study due to any reason will be considered as withdrawal.

Subject wise data listings will be sorted by subject number; listing will include subject number, treatment, reason for discontinuation, discontinuation period, date & time.

### **14.0 Protocol Deviations/Violation**

Protocol Deviation is defined as less serious non-compliance which needs adequate documentation and Protocol Violation is defined as serious non-compliance with the protocol resulting in the exclusion of a randomized subject from the study. Listing will be provided for subjects with protocol deviation/violation in the study.

### **15.0 Handling of data from visit**

Tabulation of descriptive statistics will be performed primarily using SAS® (release 9.4 or higher).

### **16.0 Safety Analyses**

Safety analyses will be performed on safety population set (refer section 6.2). All safety data will be listed by subject, treatment group and parameter, separate listings of all abnormal laboratory findings will be provided, and clinically significant abnormalities will be recorded as AEs.

#### **16.1 Adverse Events**

Adverse events (AEs) will be mapped to preferred term and body-organ system using MedDRA™. The number and percentage of subjects reporting AEs will be

summarized by AE preferred term and AE body-organ system. Adverse events will be summarized by severity and relationship to study drug also.

In particular, AE summary tables will be presented for the following:

- AE overview
- AE incidence
- AEs by severity
- AEs leading to study drug discontinuation
- AEs by relationship

Each participant will be counted only once within each summation level (SOC; preferred term). If a participant experiences more than one AE within each summation level only, the AE with the strongest relationship or the maximum severity, as appropriate, will be included in the summaries of relationship and severity.

Adverse events will be attributed to the most recent dose taken, i.e., AEs occurring post-dose but prior to the next dose, will be attributed to the most recent dose by using the date and time the AE occurred. Adverse events occurring after the first dose of study drug are considered treatment emergent.

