## **6 STUDY VISIT SCHEDULE AND ASSESSMENTS**

Following review of all Screening procedures, eligible subjects will be enrolled into the dosing phase of the study. The interval between screening and first treatment may be up to 30 days. Eligible subjects will check into the clinic on the day before each treatment and are required to stay approximately 36 hours at the clinic for preparation, dosing and follow-up assessments for each dosing period. The washout period following each dose must be a minimum of 48 hours until the next dose. Subjects will be required to stay in the clinic for the entire duration of the study (unless medically necessary to leave the clinic as instructed by the principal investigator).

All procedure times listed are approximate and are provided as a guide. The PK samples should be drawn as close as possible to the specified time. Vital signs should be taken within a time frame that will allow the PK blood sample to be drawn on schedule. Actual times of procedures for each subject may vary depending on scheduling and will be recorded on the CRF.

Subjects will refrain from smoking or using tobacco products during each clinic stay. Consumption of unsweetened coffee and tea in moderate amounts will be permitted. Breakfast can be served approximately two hours post-dosing, lunch approximately 4-6 hours after dosing and dinner will be served approximately 8-10 hours after dosing.

AEs and concomitant medication usage will be assessed throughout the study from the first day of study patches application until the Final Visit (or Early Termination) procedures are completed.

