#### **6.4 End of Study Visit/or Early Termination**

- Within 48 hours after completion of all protocol required procedures on the last dosing day, subjects will complete an End of Study Visit. At that time, the following assessments will be performed:
- Record all AEs, whether observed by investigator, reported by the subject, observed in laboratory findings, or discovered by other means, on the AE CRF through the end of study final visit.
- Record a 12-Lead ECG
- Record any new concomitant medications and adverse events
- Measure vital signs (inclusive of temperature)
- Perform a physical examination
- Measure body weight
- Investigator visual skin assessment of the application sites
- Collect blood and urine for laboratory tests and serum pregnancy test (for all females)
- Dismiss subject from the study

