## **8.2 Documentation and Reporting of Adverse Events By the Investigator**

All adverse events (AEs) occurring after the application of the first dose through the End of study visit/or early termination, will be reported on the AE CRF pages. Based on the medical judgement of the investigator, all non-serious systemic and skin AEs will be followed until 30 days after the final end of study visit. All non-resolved, non-serious systemic and skin AEs beyond such date will be recorded as 'ongoing' without further follow up.

However, an AE form will not be filled out for subjects who sign the ICF but fail the entry criteria (Screening failures) during the Screening process and experience a non-serious AE.

Application site reactions will be reported on a dedicated assessment form for the visual skin assessment of the application sites. The regular AE form does not have to be completed for such events unless the events are not covered by the questions on the visual skin assessment form or are reported outside their time window. However, all such events will be included in the analyses of adverse event incidence.

Each AE, including skin AEs, is to be assessed to determine if it meets the criteria for an SAE. If an SAE occurs, expedited reporting will follow local and international regulations, as appropriate (See [Section 8.4](#)). It should be noted that the form for collection of SAE information is not the same as the AE CRF. Where the same data are collected, the forms must be completed in a consistent manner. For example, the same AE term should be used on both forms. Systemic and skin AEs should be reported using concise medical terminology on the CRF pages as well as on the form for collection of SAE information.

In addition to recording the signs, symptoms or diagnosis associated with them to describe the adverse event, the following will also be assessed and recorded:

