## **4.0 Study Description**

### **4.1 Randomization and Blinding**

The 24 subjects are planned to receive each of the four treatments (A, B, C, D) 48 hours apart.

The order of receiving of the investigational products for each subject will be determined according to a randomization schedule which will be appropriate to the study design. Subjects will be randomized to one of the four sequences: either ABCD or BDAC or CADB or DCBA. Equal allocation of the sequence will be ensured.

The randomization schedule will be generated using SAS® statistical software (Version: 9.4; SAS Institute Inc, USA), by a biostatistician of Clianza Research Limited. The randomization schedule will be maintained under controlled access.

The personnel involved in the dispensing of investigational products will be accountable for ensuring compliance to randomization schedule.

At the end of each dosing day, the safety data from the subjects will be evaluated. If tolerability is deemed to be acceptable by the Principal Investigator, a decision will be made to proceed to the next dosing day.

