## 4.5 Study Design, Treatment and Plan

This is a single-center, open-label, randomized, four-way crossover study. Each subject will receive each of the four study treatments once, followed by in-clinic monitoring and extensive blood sample collection for pharmacokinetic analysis.

Dosing will occur approximately 48 hours apart, until completion of dosing in randomized order per the treatment sequence tables. Plasma samples from the dosing days will be sent to the analytical laboratory for analysis and tolerability for each of the dose levels will be summarized.

After completion of the four dosing days, subjects will be assessed one final time and dismissed from the study.

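### SAP 16.1 attributes adverse events by onset time alone, so a patch-site event that begins after the next dose is tabulated under a different treatment, in some cases the nasal spray

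*SAP*

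**What the plan says.** SAP 16.1 states: "Adverse events will be attributed to the most recent dose taken, i.e., AEs occurring post-dose but prior to the next dose", and that such events "will be attributed to the most recent dose by using the date and time the AE occurred". No other section overrides this for events at a patch site.

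The interval between doses is short. SAP 4.5: "Dosing will occur approximately 48 hours apart, until completion of dosing in randomized order per the treatment sequence tables". Protocol section 6: "The washout period following each dose must be a minimum of 48 hours until the next dose". SAP 4.1 fixes the orders: "Subjects will be randomized to one of the four sequences: either ABCD or BDAC or CADB or DCBA", with equal allocation of 24 subjects. A and C are upper-arm patches worn for 30 and 60 minutes, B is the thigh patch, and D is the nasal spray.

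Protocol 8.2 puts application-site reactions on a dedicated skin form. The regular adverse event form is not needed "unless the events are not covered by the questions on the visual skin assessment form or are reported outside their time window". The same section says that all these reactions enter the adverse event incidence analysis. Mock Tables 14.3.1.1 to 14.3.1.4 report adverse events in columns A to D. Listing 16.2.7 shows drug, dosing time and period, but not the body site.

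Skin scores are handled separately. SAP 16.4 summarizes them by treatment up to 24 hours. A further "Investigator visual skin assessment of the application sites" takes place at the End of Study visit (Protocol 6.4).

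**The concern.** In this design, location can identify the treatment better than timing does. Only B is applied to the thigh, and D leaves no patch site. A thigh reaction that begins after a later dose still comes from B, and a reaction at any patch site cannot come from D. Under a rule based on time alone, such an event goes to whichever treatment was given last.

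If this happens, the patch that caused the event loses it from its adverse event rate, another treatment gains it, and the spray can appear to have caused application-site reactions. That touches the tolerability comparison with the spray (Objective 3) and the adverse event part of the arm-versus-thigh comparison (Objective 1). Local reactions that the skin form does not grade, such as itch or rash, are the most exposed because they are captured only as adverse events.

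**Working it through.** The plan states no figure to reproduce. It has no sample size calculation, and the point concerns a rule. The check is therefore a count of exposed dosings.

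**Inputs**
- Sequences: "either ABCD or BDAC or CADB or DCBA" (SAP 4.1).
- 24 subjects in four equal groups: 24/4 = 6 per sequence.
- Patch treatments A, B, C: 24 × 3 = 72 planned patch dosings.

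**Patch dosings followed by another dose**

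| Sequence | Patch dosings with a later dose | Next treatment |
|---|---|---|
| ABCD | A, B, C | B, C, D |
| BDAC | B, A | D, C |
| CADB | C, A | A, D |
| DCBA | C, B | B, A |

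- Total: (3 + 2 + 2 + 2) × 6 = 54 of 72 (75%), or 18 each for A, B and C. The next treatment is always a different one.
- Next treatment is D: C in ABCD, B in BDAC, A in CADB, so 3 × 6 = 18. This affects 18 of 24 subjects, since DCBA gives the spray first.
- Next treatment is another patch: 54 − 18 = 36. Of these, 12 are upper arm directly after upper arm (A to C in BDAC, C to A in CADB: 2 × 6). There, knowing only that the event is on the upper arm does not separate the treatments.

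**Largest effect of one event**
- One subject of 24: 1/24 = 4.2 percentage points.
- Removed from one treatment and added to another: 2/24 = 8.3 points on the difference.
- These are maxima. SAP 16.1 counts a subject once per term, so nothing is lost if the subject already has that term under the true treatment, and nothing is gained if the subject already has it under the other.

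**Illustration of frequency**

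The documents give no rate for site events that begin after the next dose. Assume a rate p per exposed dosing, independent across dosings, with p from 1% to 10%. The expected number misassigned is 54p overall and 18p to D. The chance of at least one under D is 1 − (1 − p)^18.

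| Assumed p | Expected, all | Expected, to D | Chance of at least one under D |
|---|---|---|---|
| 1% | 0.54 | 0.18 | 17% |
| 5% | 2.7 | 0.9 | 60% |
| 10% | 5.4 | 1.8 | 85% |

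**What the rule cannot reach**

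Skin scores at patch removal, 12 hours and 24 hours all precede the next dose and are tabulated by treatment without using the attribution rule.

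**The case against.** The best defense is that the gap is narrow and may never matter.

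- **Timing.** An event must begin about 48 hours or more after application to be misassigned. Protocol 4.3 and SAP 5.2 say that earlier adverse events nearly all arose in the minutes just after application. This stands and limits the likely count. However, that experience is with 30-minute upper-arm application, not the thigh or one-hour wear.
- **Onset, not report.** A reader might infer that in sequence ABCD any site reaction first reported at End of Study goes to D. The documents do not support this. SAP 16.1 uses when the event occurred, and Protocol 8.2.1 has the start date and time recorded. Only onset after the D dose is affected.
- **Skin follow-up.** A reader might also infer that skin observation stops at 24 hours. It does not: Protocol 6.4 and 7.3.4 schedule a check at End of Study, and the mock skin tables carry a 48-hour column.
- **Objective 1.** The irritation signs it names are the four that the skin form grades, and those scores to 24 hours are safe. This stands.
- **Traceability.** The investigator rates causality for every event, and a site reaction listed under a nasal spray would stand out. This helps only in part. A causality rating does not move an event between columns, and an event moved from one patch to another would not stand out, because Listing 16.2.7 has no site column.
- **Attributing by site is not trivial.** A and C share the upper arm, and nothing requires different positions across periods. The vial labels in Protocol Appendix 3 distinguish the two patches of one dosing and need not separate A from C. This stands, and the fix has to deal with it.

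**Conclusion.** The point holds within limits. Followed as written, SAP 16.1 places a patch-site event with onset after the next dose under a different treatment. For thigh sites, and whenever the later treatment is D, the assigned treatment could not have caused it. Of 72 planned patch dosings, 54 are exposed, and in 18 the next treatment is the spray.

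The consequence is confined to the descriptive adverse event incidence, severity and causality tables. A reader might go further and conclude that the arm-versus-thigh irritation comparison is compromised. The documents do not support that, because the by-treatment skin scores to 24 hours do not depend on this rule.

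The size is at most 4.2 points on one treatment's rate and 8.3 points on a difference per misassigned subject. This assumes 24 subjects dosed per treatment, equal allocation, and a subject with no other event of that term under either treatment. The number of such events is unknown and may be small; the 1% to 10% range above is an assumption.

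One further rule could widen the gap slightly. SAP 16.1.1 treats an onset with a known date but no time as post-dose. If that is read as after that day's dose, a site reaction noticed before dosing could also move to the new treatment.

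**What to change.** Change SAP 16.1 before it is finalized, along these lines:

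> Adverse events located at a patch application site are attributed to the treatment and period in which a patch was applied at that site, whatever the onset time. All other adverse events are attributed to the most recent dose.

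To make the rule workable:
- Record site, side and position for every patch application in each period, and for each application-site adverse event.
- Add a site column to Listing 16.2.7.
- Where an upper-arm event cannot be separated between A and C because the position was reused or not recorded, attribute it to the most recent patch dosing on that arm, never to B or D, and flag it in the listing.

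The cost is one SAP rule and a small CRF and listing addition, with no extra visit or procedure. Some upper-arm events may remain uncertain between A and C, but they would be visible as such.
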